5.4.1.5. Q-LES-Q

The Quality of Life, Enjoyment, and Satisfaction Questionnaire (Q-LES-Q) is a 16-item self-administered questionnaire designed to measure degree of enjoyment and satisfaction in general activities. The Q-LES-Q measures each of the items using a 5-point Likert-type scale as: 1=very poor; 2=poor; 3=fair; 4=good; 5=very good. The scoring of the Q-LES-Q involves summing only the first 14 items to yield a raw total score. The last 2 items are not included in the total score but are stand-alone items. The raw total score ranges from 14 to 70. The raw total score is transformed into a percentage maximum possible score using the following formula:

$$100 * \frac{(\text{raw total score} - \text{minimum possible raw score})}{(\text{maximum possible raw score} - \text{minimum possible raw score})}$$

The minimum possible raw score on the Q-LES-Q is 14, and the maximum possible raw score is 70. Higher Q-LES-Q scores reflect greater enjoyment and satisfaction with general activities.

5.4.1.6. Self-Assessment of Treatment Experience

The Self-Assessment of Treatment Experience questionnaire is a 4-item self-report scale designed to provide additional information regarding the subject's subjective experience while taking the treatment.

5.4.1.7. HDRS₁₇ total score in subjects with comorbid MDD

The HDRS₁₇ total score will be calculated as described in Section 5.3.1.7, for subjects with comorbid MDD.

5.4.1.8. HDRS₁₇ anxiety/somatization factor score in subjects with comorbid MDD

The HDRS₁₇ anxiety/somatization factor score will be calculated as described in Section 5.3.1.8, for subjects with comorbid MDD.

5.4.1.9. HAM-D₆ score in subjects with comorbid MDD

The HAM-D₆ score will be calculated as described in Section 5.3.1.9, for subjects with comorbid MDD.

5.4.1.10. SIGH-A total score in subjects with comorbid GAD

The SIGH-A total score will be calculated as described in Section 5.3.1.5, for subjects with comorbid GAD.

5.4.1.11. HAM-A₆ score in subjects with comorbid GAD

The HAM-A₆ score will be calculated as described in Section 5.3.1.6, for subjects with comorbid GAD.

5.4.1.12. HDRS₁₇ ≥50% improvement from baseline on total score in subjects with comorbid MDD

The percentage change from baseline is calculated as

$$100 * \frac{(\text{HDRS}_{17} \text{ total score at any time point} - \text{HDRS}_{17} \text{ total score at baseline})}{\text{HDRS}_{17} \text{ total score at baseline}}$$

A ≥50% improvement on HDRS₁₇ total score means that the percentage change from baseline is ≤ -50 in this calculation. The HDRS₁₇ ≥50% improvement will be calculated for subjects with comorbid MDD.

5.4.1.13. HDRS₁₇ ≥30% improvement from baseline on total score in subjects with comorbid MDD

The HDRS₁₇ ≥30% improvement on total score will be calculated for subjects with comorbid MDD in a similar manner as described in Section 5.4.1.12

5.4.1.14. SIGH-A ≥50% improvement from baseline on total score in subjects with comorbid GAD

The SIGH-A ≥50% improvement will be calculated as described in Section 5.3.1.11, for subjects with comorbid GAD.

5.4.2. Analysis Methods

For all continuous exploratory endpoints, descriptive statistics of actual values and changes from baseline at each scheduled time point and endpoint will be provided by treatment group (mean, SD, median and range). A mean-SE plot over time will be presented for the observed values by treatment group. This includes SDS total score, GAD total score, SHAPS total score, MOS Sleep-R, Q-LES-Q percentage maximum possible score, HDRS₁₇ total score, HDRS₁₇ anxiety/somatization factor score, HAM-D₆ score, SIGH-A total score and HAM-A₆ score.

Frequency counts and percentages will be provided at each scheduled time point and endpoint by treatment group for the following variables: Q-LES-Q last 2 items, Self-Assessment of Treatment Experience scale, HDRS₁₇ $\geq 50\%$ improvement, HDRS₁₇ $\geq 30\%$ improvement and SIGH-A $\geq 50\%$ improvement.

6. PHARMACOGENOMIC ANALYSES

It is recognized that genetic variation can be an important contributory factor to interindividual differences in drug distribution and response and can also serve as a marker for disease susceptibility and prognosis. Pharmacogenomic research may help to explain interindividual variability in clinical outcomes and may help to identify population subgroups that respond differently to a drug. The goal of the pharmacogenomic component is to collect DNA to allow the identification of genetic factors that may influence PK, PD, safety, and/or tolerability of JNJ-42165279 and to enable the development of safer, more effective and ultimately individualized therapies in the future. DNA samples will be analyzed for the FAAH gene. Additional analyses may be conducted if it is hypothesized that this may help resolve issues with the clinical data.

DNA samples will be used for research related to JNJ-42165279. They may also be used to develop tests/assays related to JNJ-42165279. Pharmacogenomic research may consist of the analysis of one or more candidate genes or of the analysis of genetic markers throughout the genome (as appropriate) in relation to JNJ-42165279 clinical endpoints. Analyses may be performed across multiple clinical studies.

The relationship between genetic subgroups for the FAAH gene (C/C or A/C) and JNJ-42165279 biomarker endpoints (AEA, PEA and OEA) will be examined through descriptive statistics and graphical presentations. A similar analysis will be performed to explore the relationship between genetic subgroups and the LSAS total score.

7. BIOMARKERS

Biomarker analyses will be based on the safety analysis set, which will include all randomized subjects who receive at least one dose of study medication (either placebo or JNJ-42165279).

During the study, the following biomarker evaluations will be performed at Day 1, Day 28 and Day 84/ end of withdrawal visit: plasma concentrations of FAAs (AEA, PEA and OEA).

Descriptive statistics of actual values and changes and percent changes from baseline for concentrations of AEA, PEA and OEA at each scheduled time point and endpoint will be provided by treatment group (mean, SD, median and range). A mean-SE plot over time will be presented by treatment group, and results will be listed.

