A preliminary analysis of data from study 42165279EDI1002 indicates that the plasma pharmacokinetics of JNJ-42165279 in female subjects and elderly subjects are similar to each other and to healthy male subjects enrolled in study 42165279EDI1001. These 3 subject groups received a single 100-mg dose of JNJ-42165279 and once-daily administration of the same dose until steady-state conditions were achieved.

Pharmacodynamic measures revealed that across the 25- to 100-mg JNJ-42165279 dose range, FAAH activity in WBCs was suppressed attaining a mean nadir of 7.85% to 10.4% (relative to predose values) after a single dose and a mean nadir of 0.58% to 10.5% after once-daily dosing for 10 days. At 96 hours after the last dose, mean FAAH activity remaining ranged from 28.3% to 58.2% of predose values. Single doses of JNJ-42165279 in the range of 25 to 100 mg produced mean peak concentrations of AEA in plasma that were 5.5- to 10-times higher than mean predose values, whereas mean peak OEA and PEA concentrations 4.3- to 5.6-times higher. Similar changes in mean FAA concentrations were observed after daily administration of 25 to 100 mg for 10 days. Mean plasma AEA, OEA, and PEA concentrations were 1.3- to 3.1-times higher than mean predose values at 96 hours after the last JNJ-42165279 dose. Daily administration of JNJ-42165279 for 7 days increased mean AEA and OEA concentrations in CSF by approximately 41-times and 5.8-times (25 mg dose), respectively, and 77-times and 7.4-times (75 mg dose), respectively, relative to predose. The concentrations of AA in CSF were unchanged.

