## 9.5.3. Pharmacokinetic Parameters

PK analyses of the plasma concentrations will be undertaken to estimate peak plasma concentration and systemic exposure of JNJ-42165279. Based on the individual plasma concentration-time data, if sufficient data are available, the following PK parameters of JNJ-42165279 will be estimated at steady state in subjects receiving a dose of JNJ-42165279 using population PK modeling:

C max	maximum plasma concentration
t max	time to reach the maximum plasma concentration
$AUC_{\tau}$	area under the plasma concentration-time curve from 0 to $\tau$ hours post dosing (time $\tau$ is the dosing interval)

The parameters of interest for the statistical analysis will be the log-transformed estimated dose normalized AUC and  $C_{max}$ . All ratios will be calculated as differences of least square means of the appropriate model on the log-scale, and will be presented after back-transformation to the original sale with the corresponding 90% confidence intervals (CIs).

Based on the individual plasma concentration-time data, using the actual dose taken and the actual sampling times, PK parameters and exposure information of JNJ-42165279 will be derived using population PK modelling. Baseline covariates (e.g., body weight, age, sex, CrCL, race) may be included in the model, if relevant.

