2.3.3. Baseline

Baseline is defined as the last non-missing observation prior to first dose of study drug.

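### In SAP Section 7, mean percent change modestly overstates the rise in AEA, PEA and OEA, and no drug/placebo ratio with an interval is planned

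*SAP*

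**What the plan says.** SAP Section 7 measures the fatty acid amides at "Day 1, Day 28 and Day 84/ end of withdrawal visit: plasma concentrations of FAAs (AEA, PEA and OEA" and bases the analysis on the safety set. It reports "Descriptive statistics of actual values and changes and percent changes from baseline for concentrations of AEA, PEA and OEA", which "will be provided by treatment group (mean, SD, median and range" among the listed statistics. For the graph, "A mean-SE plot over time will be presented by treatment group, and results will be listed". The section states no log transformation, geometric mean, ratio to baseline, between-arm estimate or confidence interval.

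The denominator of percent change is set in SAP Section 2.3.3: "Baseline is defined as the last non-missing observation prior to first dose of study drug". The protocol's Time and Events Schedule has a single pre-dose fatty acid amide sample, at Visit 2, so the baseline is one measurement.

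Two parts of the protocol already work in ratios. Section 1.1 (Clinical Studies) reports, after single doses of 25 to 100 mg, "mean peak concentrations of AEA in plasma that were 5.5- to 10-times higher than mean predose values". Section 9.5.3, on drug AUC and Cmax, says "All ratios will be calculated as differences of least square means of the appropriate model on the log-scale" and gives back-transformed results with 90% intervals. Protocol Sections 11.6 and 11.7 add concentration-biomarker plots and, if judged appropriate, population PK/PD models.

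**The concern.** These analytes are positive plasma concentrations that are expected to change by multiples. Percent change cannot fall below −100% but has no upper limit. If a subject's single baseline happens to be low, that subject's percent change is inflated by more than an equally high baseline would deflate it. Averaged over subjects, the mean drifts upward even when nothing has changed.

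What is at stake is how accurately the size of the pharmacodynamic effect is reported. The fatty acid amides are the only marker of FAAH inhibition scheduled in this trial; Phase 1 also measured FAAH activity in white blood cells. A published mean percent change would be somewhat too large in both arms. Readers would also have no drug/placebo estimate with an interval to set beside it, although evaluating pharmacodynamic effects is a stated exploratory objective. SAP Section 6 compares the same biomarkers between FAAH genotypes, again descriptively and with no scale stated.

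**Working it through.** **Plan's own figure.** There is none to reproduce. The documents give no CV, SD, target fold-rise or power for the fatty acid amides.

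**Inputs.**
- True fold F: 1 for placebo. For drug, 5.5 and 10, the ends of the Phase 1 plasma AEA range in Protocol Section 1.1, used only as illustrations.
- Within-subject CV: 20%, 30%, 40% and 50%. These are assumptions.
- Distribution: log-normal, with independent errors at the two visits and the same CV at each. Also an assumption.

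**Formula.** Let X be the baseline and Y the post-dose value of one subject, and let s² = ln(1 + CV²) be the within-subject variance on the log scale. The subject's own level cancels in Y/X, which leaves

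E(Y/X) = F × exp(s²) = F × (1 + CV²).

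The expected mean percent change is therefore 100 × [F × (1 + CV²) − 1]. The population median percent change is 100 × (F − 1), which is free of the CV.

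**Results.**

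| CV | 1 + CV² | Placebo mean % change (true 0) | F = 5.5, mean % change (true 450) | F = 5.5, apparent fold | F = 10, mean % change (true 900) |
|---|---|---|---|---|---|
| 20% | 1.04 | +4 | +472 | 5.72 | +940 |
| 30% | 1.09 | +9 | +499.5 | 6.00 | +990 |
| 40% | 1.16 | +16 | +538 | 6.38 | +1060 |
| 50% | 1.25 | +25 | +587.5 | 6.88 | +1150 |

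**Simulation check.** This used 4,000 runs, 60 subjects per arm and an assumed between-subject CV of 40%. Ranges are over the four within-subject CVs.

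| Summary | Placebo | Drug, F = 5.5 |
|---|---|---|
| Mean % change | 4.1, 9.0, 15.9, 25.0 | 472.1, 500.8, 537.8, 588.1 |
| Median % change | 0.1 to 0.7 | 451.1 to 452.5 |
| Mean raw change | −0.001 to 0.001 | not a fold measure |
| Ratio of arithmetic means | 1.001 to 1.005 | 5.506 to 5.521 |
| Geometric mean ratio | 1.001 to 1.003 | 5.504 to 5.518 |

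So the bias sits in mean percent change and nowhere else in the planned list.

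**Comparing arms.** If the CV is the same in both arms, the factor cancels in the ratio of mean folds. At CV 30% the simulated values give (500.8 + 100) / (9.0 + 100) = 5.51. It does not cancel in a difference of mean percent changes. At CV 30% the closed form gives 499.5 − 9 = 490.5 points against a true 450, and at CV 50% it gives 587.5 − 25 = 562.5.

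**The case against.** The case for leaving the plan alone is substantial, and most of it stands.

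- **The median is already planned.** Median percent change, for the same quantities and by arm, is nearly free of the bias. This stands. It comes without an interval or a between-arm contrast, but that is a lack of precision information and not a bias.
- **The Phase 1 multiples compare mean concentrations.** The planned means of actual values reproduce that metric without this bias. This stands. The SAP itself reports no fold-rise; an inflated fold appears only if a reader converts the mean percent change.
- **The size rests on an assumed CV.** This stands, and is why a range is shown.
- **Section 9.5.3 concerns drug AUC and Cmax, not biomarkers.** This stands. It is a precedent for a ratio scale and does not contradict SAP Section 7.
- **The objective is exploratory, and a modelled ratio would be a new analysis.** This also stands. The proposal is an improvement, to be labelled exploratory.
- **PK/PD modelling is foreseen.** This stands only in part. Protocol Sections 11.6 and 11.7 make it optional and commit to no drug/placebo estimate.

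A reader might go further and infer that all the raw-scale summaries create a false placebo rise. The simulation rules that out for arithmetic means, raw changes and the median. A reader might also infer that the bias could mislead about why a negative LSAS result occurred, by confusing failed exposure with a failed mechanism. The documents do not support that. Exposure is measured directly, with drug concentrations at Days 14 and 28 (Time and Events Schedule, footnote m), population PK (Protocol Section 11.7) and a sensitivity analysis based on PK compliance criteria (SAP Section 2.6). An apparent rise of 25% is also far from one of several hundred percent.

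**Conclusion.** This is a minor reporting point that is worth fixing. Mean percent change in SAP Section 7 is biased upward by a factor of 1 + CV² on the fold scale. That factor is 1.04 to 1.25 for an assumed within-subject CV of 20% to 50%, under independent log-normal errors with equal CV at both visits. Positive correlation between the errors would reduce it, and a larger CV would increase it.

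The question of whether 25 mg raised the fatty acid amides would be answered the same way with or without the change, and no efficacy conclusion depends on it. What the change improves is the reported size of the effect and, more usefully, the availability of a drug/placebo ratio with its uncertainty, which nothing in the plan commits to.

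**What to change.** In SAP Section 7, for AEA, PEA and OEA:

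1. Analyse natural-log concentrations.
2. Report geometric means with CV by arm and visit, and the geometric mean ratio to baseline with a confidence interval.
3. Estimate the JNJ-42165279/placebo ratio with a 95% confidence interval at Day 28 and Day 84, from a model on log concentration with log baseline as covariate. Label it exploratory.
4. Plot geometric means on a log axis.
5. Keep the median and range. Drop mean percent change, or replace it with the geometric mean percent change, 100 × (geometric mean ratio − 1).

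The cost is a revised paragraph in the SAP and a little extra programming. No new samples or data are needed.

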8. SAFETY

All safety analyses will be based on the safety analysis set, which will include all randomized subjects who receive at least one dose of study medication (either placebo or JNJ-42165279).

All safety data will be listed for the subjects in the safety analysis set.

8.1. Incomplete/Missing Dates for Adverse Events

A conservative approach will be used to handle the missing dates for adverse events. The rules for estimating incomplete AE onset dates will be as follows:

- (1) The missing day of the month will be estimated as follows: If the month and year are known and double-blind study medication started during that month then the estimated date is the start date of double-blind study medication. If the month and year are known and double-blind study medication started prior to that month then the estimated date is the 1st day of the month. If the month and year are known and double-blind study medication started after the month, then no estimation will be done, and the AE will not be considered as treatment emergent for the double-blind phase.
- (2) If both the day and the month are missing: No estimation will be performed. However, these AEs will be considered treatment emergent for the double-blind phase and will be included in the double-blind treatment summaries, except for the calculation of duration of the AE. Attempts will be made to get at least the month for the adverse events.

The rules for estimating incomplete AE onset times will be as follows:

The missing times will be estimated as follows: use time 00:00:00 of the given/imputed date for the start date/time of an AE and use 23:59:59 for the end date/time of an AE.

For incomplete AE resolution dates, the rules are:

- (3) The missing day of the month will be estimated as follows: If the month and year are known and the study medication was stopped before, or during that month, the estimated date is the last day of the month or the end of the double-blind phase, whichever is earlier. If the study medication stopped after that month then the estimated date is the last day of the month.

If both the day and the month are missing: the estimated resolution date is the end of the double-blind phase.

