## 6. DOSAGE AND ADMINISTRATIONa

Study medication will be provided as JNJ-42165279 tablets, strengths 25 mg and matching placebo, packaged in bottles. All tablets (JNJ-42165279 /placebo) are physically identical.

A study-site investigational product manual including instructions for dispensing, storage (on site and at home) and intake of the study medication will be supplied to the study-site.

Study-site personnel will instruct subjects on how to store study drug for at-home use as indicated for this protocol. The sponsor may optionally develop tools to improve and/or document compliance to intake of study medication when locally feasible. This may include a diary or an electronic registration tool.

The selected 25 mg dose of JNJ-42165279 is expected to result in complete inhibition of FAAH enzyme in the brain throughout the dosing interval based on the outcome of the single ascending dose (42165279EDI1001), multiple ascending dose (42165279EDI1002) and PET occupancy (42165279EDI1003) studies.

During the treatment phase of this study dispensing and redispensing of their study medication will take place at the visits indicated in the Time and Events schedule. On Days of re-dispensing subjects will hand in their medication package dispensed previously and drug accountability will be performed.

Following last dosing, subjects will hand in their study medication received previously and final drug accountability will be performed.

During the entire blinded treatment period subjects will self-administer once-daily (q.d.) study drug (JNJ-42165279/placebo) with a glass of non-carbonated water, after completion of breakfast or a light snack, during the morning hours, according to the instructions provided by the investigator. During scheduled visits subjects will self-administer their study medication on site as described above which will be witnessed by designated study-site personnel at the study sites. On Day 1 study drug administration will be administered following completion of all predose assessments and will not be limited to the morning hours.

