8.2. Adverse Events

The verbatim terms used in the CRFs by the investigator to identify adverse events (AEs) will be coded using the current Medical Dictionary for Regulatory Activities maintained by the sponsor.

Therapeutic reach is the number of days after the last dose intake that a subject is still considered to be potentially affected by study drug. For JNJ42165279, therapeutic reach is defined as 4 days. AEs will be summarised using the therapeutic reach. Therapeutic reach will only be applied to the end of double-blind treatment period or to subjects who discontinue.

A treatment-emergent AE (TEAE) is an event that is new in onset or increased in severity following treatment initiation. Any event with a start date and time after the first dose intake will be considered treatment-emergent. An event that starts prior to and ends after the initiation of study medication will be considered treatment-emergent only if the severity increases after the start of medication. An event that starts in the follow up period but within the therapeutic reach of 4 days will be considered treatment-emergent. Adverse events with onset date during the follow-up phase outside the therapeutic reach of 4 days will be summarized separately.

The number (%) of subjects with TEAEs will be summarized by system organ class and preferred term for each treatment group. A summary will be created for the most common TEAEs ($\geq 5\%$ incidence in either treatment group). In addition, TEAEs will be summarized by severity and relationship to study drug for each treatment group by system organ class and preferred term. For the summaries of AEs by severity/relationship to study drug, the observation with the most severe occurrence/closest relationship to study drug will be chosen if there is more than one incident of an adverse event reported during the treatment phase by the subject.

TEAEs will also be summarized by sex, by country, and by enrollment prior to/after study suspension.

Serious AEs (SAEs) and TEAEs that lead to study discontinuation will be summarized separately by treatment group, system organ class and preferred term.

Treatment-emergent headaches, TEAEs related to liver function test abnormalities and TEAEs of special interest (diplopia, vision impairment, gait disturbance, severe headache) will be presented graphically over time for each individual subject.

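### Setting a missing adverse event onset time to midnight places two kinds of event before the first dose and takes them out of the treatment-emergent tables, against the SAP's stated conservative approach

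*SAP*

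**What the plan says.** SAP Section 8.1 opens with its aim: "A conservative approach will be used to handle the missing dates for adverse events". For an onset whose day is missing but whose month and year are known, rule (1) has three branches:

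- Dosing began in that month: "then the estimated date is the start date of double-blind study medication".
- Dosing began in an earlier month: the onset is set to the first of the month.
- Dosing began in a later month: no date is estimated and the event is not treatment-emergent.

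Rule (2) covers onsets with both day and month missing. No date is estimated, but "these AEs will be considered treatment emergent for the double-blind phase".

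A separate rule handles missing onset times: "use time 00:00:00 of the given/imputed date for the start date/time of an AE". It makes no exception for the date of first dose.

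SAP Section 8.2 defines a treatment-emergent AE by date and time together: "Any event with a start date and time after the first dose intake will be considered treatment-emergent". An event that starts before the first dose and continues past it counts only if it becomes more severe.

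Protocol Section 6 fixes when the first dose is taken: "On Day 1 study drug administration will be administered following completion of all predose assessments". Protocol Section 9.1.3 says the same for the Day 1 clinic visit.

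**The concern.** Each rule is reasonable alone, but the time rule undoes the date rule. Moving an onset with an unknown day to the first-dose date serves no purpose unless the event then counts as treatment-emergent. Midnight on that date is before the dose, so the event fails the Section 8.2 test. The same happens to an event correctly dated Day 1 with no clock time. An event with less date information (day and month both missing) is counted, while one with more is not.

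The tables by treatment group are the main display for safety and tolerability, a secondary objective. The treatment-emergent definition feeds the summaries by system organ class and preferred term, the table of common events, the summaries by severity and by relationship, the summary of events leading to discontinuation, and the graphs of headaches and events of special interest. Reactions to the first dose would fall on Day 1.

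**Working it through.** The plan gives no figure to reproduce, so the check applies the rules as written.

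**Inputs.** Date and time rules: SAP Section 8.1. Treatment-emergent test: SAP Section 8.2, onset date/time > first-dose date/time. Position of the first dose: Protocol Sections 6 and 9.1.3. The documents give no clock time for the dose. For illustration, assume a first dose on 14 November at 10:00.

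| Onset information | Onset assigned | Result as written | Result with the fix |
|---|---|---|---|
| Day 1, no time | 14 Nov, 00:00:00 | Before dose; counts only if severity increases | Treatment-emergent |
| Day 1, recorded as 11:00 | 14 Nov, 11:00 | Treatment-emergent | Unchanged |
| Day 2, no time | 15 Nov, 00:00:00 | Treatment-emergent | Unchanged |
| November, day missing | 14 Nov, 00:00:00 | Before dose; counts only if severity increases | Treatment-emergent |
| December, day missing | 1 Dec, 00:00:00 | Treatment-emergent | Unchanged |
| October, day missing | None | Not treatment-emergent, by rule (1) | Unchanged |
| Day and month missing | None | Treatment-emergent, by rule (2) | Unchanged |

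Assumed dose times of 00:01, 08:00, 14:00 and 17:00 give the same result in every row. The clock time does not matter, because any dose taken after midnight is later than 00:00:00 on the same date. Two of the seven patterns are affected.

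**Other text.** Protocol Section 11.4 includes events with onset during the double-blind treatment phase, and SAP Section 2.3.5 assigns data from the Baseline visit onward to that phase. Both suggest that Day 1 events were meant to count. Neither states a rule for a missing time, so neither overrides Section 8.1.

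**What one subject is worth.** With 137 subjects randomized 1:1, 137/2 = 68.5, or about 68 per arm.

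- One subject: 1/68 = 1.5 percentage points.
- Threshold for the table of common events (at least 5% in either arm): 0.05 × 68 = 3.4, so 4 subjects are needed (4/68 = 5.9%; 3/68 = 4.4%).

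Losing one subject removes a term from that table only if one arm stands at exactly 4 and the other is below 4.

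**The case against.** The strongest reply is that this is a drafting gap with narrow reach and a clear intent. Section 8.2 compares times, which presumes that times are collected, so a missing time may be rare. Tables count subjects, so a lost event matters only if the subject has no other treatment-emergent event under that term. A term dropped from the common-event table still appears in the full table if any subject with it remains. The listings in Section 8.2 include events with onset before treatment, and the summary of serious events is not expressly limited to treatment-emergent ones. All of this stands, and it limits the size of the problem. It does not remove it: code that follows the SAP exactly will produce the wrong assignment, and the listings do not repair the comparison between arms.

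A reader might go further in three ways that the documents do not support.

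- *All partly dated events in the first month of dosing are lost.* Only a missing day in the calendar month of first dose is affected. A month of dosing usually runs into the next calendar month, where the onset is set to the first and still counts.
- *Every affected event is misclassified.* The assignment to before the dose is certain, but whether it is wrong is not. AEs are recorded from consent, and Day 1 includes predose procedures such as blood sampling, so some untimed Day 1 events, and some undated events in that month, may truly precede the dose.
- *The rule favours the drug.* It applies identically to both arms. A difference arises only if the drug causes early reactions. Headache and dizziness were among the frequent events on drug in Phase 1 (Protocol Section 1.1), which makes this plausible but does not show it for the first dose of 25 mg.

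**Conclusion.** The point holds within these limits. As written, SAP Sections 8.1 and 8.2 together always place two patterns before the first dose: (a) an onset dated Day 1 with no recorded time, and (b) an onset with the day missing in the calendar month of first dose. Events in these patterns leave the treatment-emergent tables unless their severity increases after dosing. This contradicts the announced conservative approach, the evident purpose of rule (1), and rule (2).

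Not affected are Day 1 events with a recorded time, missing-day events in later months, events missing both day and month, events that worsen after dosing, and the AE listings.

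The result rests only on the first dose falling after midnight, which the protocol secures. The number of affected events cannot be estimated, because the documents give no rate of missing times or days; it could be zero. No efficacy result or hypothesis test depends on it. It is a stated rule that gives the wrong result in by-arm safety tables, and it should be corrected.

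**What to change.** In SAP Section 8.1, add an exception: when the recorded or imputed onset date is the date of first dose and the time is missing, set the onset time to the time of first dose and count the event as treatment-emergent, unless the CRF shows that it began before dosing. Keep 00:00:00 for every other date.

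In SAP Section 8.2, make the comparison inclusive, so that an onset at or after the first dose counts. Without this change, an onset set equal to the dose time would still fail the test.

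The cost is two sentences and one line of derivation code. The downside is that a few events that truly began before dosing may be counted as treatment-emergent. The same rule would apply in both arms, and this error is in the conservative direction that the SAP says it wants.
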